Upon enrollment and completion of the informed consent process, patients will be randomized into the 2 study groups of 60 each, based on a list compiled by a random number generator prior to initiation of the study. Both Groups will complete the Western Ontario and McMaster Universities Osteoarthritis Index (WOMAC), and the Subjective International Knee Documentation Committee Subjective Score (IKDC) questionnaires prior to any treatment. Due to the invasive nature of obtaining marrow aspirate blinding of the subjects and clinicians will not be performed. Group 1 [PRP]: Will receive a single (1) intra-articular injection of PRP. Group 2 [BMC]: Will receive a single (1) intra-articular injection of BMC after obtaining informed consent. Both types of injections and all associated procedures will be performed in the clinic or lab setting with local anesthesia. Following the injection patients will be asked to complete a short questionnaire documenting the BMC or PRP collection, preparation and injection experience. Ten patients will be randomly selected from both (20 total subjects) the PRP and

BMC groups to have analysis performed on the BMC and PRP as described below. This analysis will not be performed on patients not randomly selected. In patients randomly selected after the BMC or PRP have been prepared for injection, a small sample (1 mL) of the BMC or PRP will be separated and sent to an independent lab (Biosciences Research Associates, Inc) for analysis. The PRP will be analyzed with a CBC and the BMC will be analyzed for TNC, human CD34+ hematopoietic stem/progenitor cell assay, CFU-F, plasma free hemoglobin, cell viability percent, and hemolysis percent. Evaluation, a 4 view x-ray series (long leg, lateral, sunrise, and bilateral Rosenberg), and injections will be provided at no charge to the patients. Patients will then be given standard follow-up care instructions that include no use of NSAIDS for at least 7 days and partial weight bearing on the limb for 2-3 days, followed by the initiation of a standard physical therapy program at one week following injection.

After the injection subjects will be required to complete the WOMAC and IKDC questionnaires as well as report any medications they are using via email or phone (paper method will be available on request) at 1, 3, 6, 9, 12, 18, and 24 months following the injection.

PRP protocols

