crest using a prone and posterior approach. The trocar will be rinsed with 15 mL of heparin (see MSDS heparin). A total of 50 mL of bone marrow will be drawn into a syringe containing 10 mL of anticoagulant (see appendix B – MSDS sodium citrateUSP). The filter will be rinsed with 3 mL of heparin. The bone marrow will then be filtered. From the syringe with filtered bone marrow, for patients randomly selected for analysis, 1 mL of filtered BMA will be separated and sent to a lab for analysis. The remaining bone marrow will be separated into a single concentrating device, counterbalanced and placed in a centrifuge for 2.5 minutes at 3800 RPM for separation of the bone marrow concentrate. The plasma and cell concentrate will then be separated off with a syringe and stopcock, then transferred into the concentrating accessory, counterbalanced and re-spun for 7 minutes at 3800 RPM in the centrifuge to separate the cell concentrate from the plasma. After the plasma is drawn off and swirled to resuspend, the BMC will be drawn into a syringe for injection into the patient's knee (step by step instructions found in appendix A - Technique Manual). The BMC production procedure results in 7 mL of product for patients randomly selected for analysis 1 mL will be separated and sent to a lab for analysis. Both the 1 mL of BMA and the 1 mL of BMC of patients randomly selected for analysis will be sent to an independent lab (Biosciences Research Associates, Inc) to undergo analysis for TNC, human CD34+ hematopoietic stem/progenitor cell assay and CFU-F, plasma free hemoglobin, cell viability percent, and hemolysis percent.. This sample will be packaged in the company's standard sample packaging and shipped per instructions (see appendix F – BSR Quality Evaluation Program Specimen Preparation Kit) for delivery to the lab to undergo verification testing. The treating physician will then inject the BMC into the affected knee joint following standard aseptic technique per the physician's normal standard of care. The above mentioned processes will be performed using the EmCyte GenesisCS Pure BMC®-60 ml 2015kit (product number BC60-PURE) (EmCyte Corporation, Fort Myers, Florida) which has been approved by the FDA for use BMC treatments (see Appendix E – FDA Letter). This entire process will be completed in a single patient visit. Any unused portion of a sample in the physician's office or in the lab will be disposed of through standard biohazard waste disposal systems as required by law.

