
6 Expected Risks and Benefits

Risks and Discomforts: Potential risks include those expected with any injection including syncope, dizziness, headache, nausea, tachycardia, infection (septic arthritis, phlebitis, and osteomyelitis), bleeding, or pain. Additionally the patient may experience knee stiffness or inflammation associated with the procedures. For BMA harvest, there is the potential for pain, bleeding or infection at the harvest site, as well as the possibility of retroperitoneal hematoma. The filter and the trocar from the bone marrow aspiration kit will be rinsed with heparin. Risks with the use of heparin include hypersensitivity, hemorrhaging, heparin-induced thrombocytopenia (HIT), heparin-induced thrombocytopenia and thrombosis (HITT), and delayed onset HIT and HITT. As with any research involving patients there is the inherent risk of a breach in patient confidentiality though this will be minimized through the use of subject code numbers and adherence to all HIPAA guidelines.

Benefits: Direct benefits of the study include a physician visit, x-rays and an injection of BMA and/or PRP at no cost, as well as potential pain relief, improvement of knee function, and improvement of quality of life, which all could lead to the avoidance of surgical intervention. It is also believed that the information obtained in this study will help advance treatment of osteoarthritis through the use of regenerative medicine.

7 Data Management Procedures

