All personal information is strictly confidential and no names will be disclosed except as required by law. All research information will be managed and accessible by only the named investigators and their medical staff. Data sheets will have names and identifying information replaced with a subject code to protect the confidentiality of the subject. All information provided by the subject during this project will be recorded on the appropriate forms and stored in a locked room in the AREF research facility. In addition all subject data forms will be scanned and stored, along with summary information forms, spreadsheets, and photos, in a secure password protected folder on a laptop in which only study investigators will have access to, and will be permanently deleted following any and all publications or presentations have been completed related to this research. All records related to this research will be retained in a secure location for a period of 3 years following the completion of all study related activities, at which time they will be properly destroyed.

8 Data Analysis

All data will be entered into an excel spreadsheet for analysis that will include obtaining standard measures such as means and standard deviation. Data will be analyzed as scores on the two questionnaires as well as across subsets of the individual questionnaires for function, quality of life and pain scores. Additional determinations based on medication usage and failure rates will be examined as well.

9 Statistical Considerations

A power analysis was performed to determine sample size based upon recent clinical trials comparing PRP to HA for the treatment of osteoarthritis. Analysis utilized the average of standard deviation to detect average of group mean effect at 80% power. This determined that 25 patients per group would be needed to reach statistical significance with the WOMAC and that 50 patients would be needed per group for the IKDC. Considering a potential dropout rate of 20%, 60 patients per group was chosen as the sample size.

Data will be analyzed for differences between groups using a repeated measures ANOVA design, using a significant p-value of < 0.05 for rejecting the null hypothesis. Additional subjective analysis will be performed on data involving the patient experience with regards to the injection.

10 Quality Control and Assurance

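### The seven follow-up contacts do not ask about adverse events and no harm summary by arm is planned, although the marrow-harvest and heparin risks fall only on the BMC arm

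*Combined protocol and SAP*

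**What the plan says.** **Follow-up.** Section 5 fixes the content of the seven contacts from month 1 to month 24: "subjects will be required to complete the WOMAC and IKDC questionnaires as well as report any medications they are using via email or phone". Paper is available on request. Section 5 also describes one earlier instrument: "Following the injection patients will be asked to complete a short questionnaire documenting the BMC or PRP collection, preparation and injection experience".

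**Foreseen harms.** Section 6 gives general injection risks, such as septic arthritis, that apply to both arms. It then adds: "For BMA harvest, there is the potential for pain, bleeding or infection at the harvest site, as well as the possibility of retroperitoneal hematoma". On heparin it says: "Risks with the use of heparin include hypersensitivity, hemorrhaging, heparin-induced thrombocytopenia (HIT), heparin-induced thrombocytopenia and thrombosis (HITT), and delayed onset HIT and HITT".

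**Where the heparin is used.** The BMA part of section 5 states "The trocar will be rinsed with 15 mL of heparin" and has the filter rinsed with a further 3 mL. The PRP part names sodium citrate as anticoagulant and mentions no heparin.

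**Planned analysis.** Section 8 covers questionnaire scores and subscales, then says "Additional determinations based on medication usage and failure rates will be examined as well". Section 9 plans a repeated measures ANOVA and says "Additional subjective analysis will be performed on data involving the patient experience with regards to the injection". Neither section defines, counts or tabulates adverse events.

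**Data handling and oversight.** Section 7 provides that what subjects tell the study is put on study forms and stored. Section 10 gives the principal investigator or a designated team member the monitoring of protocols and the checking of analyzed data. It does not mention adverse events.

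**The concern.** The trial compares a marrow harvest plus injection with a blood draw plus injection. A reader weighing any gain in pain or function under BMC needs to know what extra harm came with it. The protocol foresees that harm and assigns part of it to one arm only, but builds no routine question or table to show whether it occurred.

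Two features make this more than a reporting nicety. First, patients and clinicians know the treatment, so what patients mention unprompted may differ by arm. Second, dates, seriousness and outcome that nobody asked about are hard to reconstruct evenly across arms at the analysis stage. A complication might otherwise appear only as a new medication, a worse score, a failure (a term section 8 does not define) or a dropout.

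**Working it through.** The plan states no harm figure, so there is nothing to reproduce. The check has two parts: what each source of information would yield, and what full collection could show at this sample size.

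**1. Sources of harm information in the plan**

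| Source | Timing | Asks about harms? | Planned harm summary by arm? |
|---|---|---|---|
| WOMAC and IKDC (section 5) | Seven contacts | No | No; analyzed as efficacy scores |
| Medication report (section 5) | Seven contacts | Indirectly; a new drug may hint at an event | No; medication usage only |
| Post-injection questionnaire (section 5) | Once, as described | Possibly, for immediate discomfort; form not seen | Only an unspecified subjective analysis (section 9) |
| Volunteered information (section 7) | Any time | No; recorded if offered | No |
| Follow-up visits (section 3), physical therapy from one week (section 5) | During follow-up | Not stated | No |
| Failure rates (section 8) | Not stated | Failure not defined | No |

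No row both asks about harms after the procedure and leads to a summary by arm. Delayed-onset HIT/HITT, or an infection that becomes evident later, falls in that gap.

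**2. Which arm carries the extra risk**

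The harvest and both heparin rinses belong to the BMC procedure. The harvest-site, hematoma and heparin risks in section 6 therefore arise in that arm alone; the general injection risks are shared.

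**3. What complete collection could show**

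Inputs: 60 patients per group (sections 5 and 9), and the dropout allowance in section 9: "Considering a potential dropout rate of 20%, 60 patients per group was chosen as the sample size". That leaves 60 × 0.8 = 48. All event rates below are assumed, and every event is taken as captured.

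- Zero events, one-sided 95% upper limit, 1 − 0.05^(1/n): for n = 60, 0.0487 (4.9%); for n = 48, 0.0605 (6.1%).
- Zero events, upper end of the two-sided exact 95% interval, 1 − 0.025^(1/n): for n = 60, 0.0596 (6.0%); for n = 48, 0.0740 (7.4%).
- Chance of seeing no event in 60, (1 − p)^60: 55% at p = 1%, 30% at 2%, 5% at 5%.
- Commoner harms, exact (Clopper-Pearson) 95% interval: 6/60 (10%) gives 3.8% to 20.5%; 12/60 (20%) gives 10.8% to 32.3%.
- Between arms, 3/60 against 0/60: two-sided Fisher p = 0.24.

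The n = 48 figures are pessimistic for harvest harms, because most of these would be reported by month 1, before the full 24-month dropout has accrued.

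These numbers describe the sample size and do not measure the loss from not asking. They show that a harm table would be informative for commoner problems, such as those at the harvest site, and weak for rare serious ones.

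**The case against.** The case for leaving the plan alone has several parts.

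- **Volunteered events are recorded.** Section 7 covers what subjects provide during the project, and section 11 has medical data recorded and stored. This stands. A reader might infer that the trial would record no harms; the documents do not support that. These clauses concern data handling: they prompt no question and plan no summary.
- **The post-injection questionnaire may cover harvest problems.** It goes to both arms, its subject includes collection, and section 9 analyzes it. This stands for immediate effects. The form is not among the documents, so it cannot be said what it omits. As described it is given once, and later events are outside its subject.
- **Safety reporting may be set out elsewhere.** The consent form and appendices were not available, and section 11 refers to an approved, stamped consent document, which implies an approving body with its own rules. A reader might infer that safety review or event reporting is absent; that cannot be concluded. Individual reporting would still not supply the table missing from sections 8 and 9.
- **The objective is effectiveness in pain and function.** True, and the efficacy comparison is untouched. But section 2's aim is to help choose between two procedures that differ in invasiveness.
- **Sample size is the real limit for rare harms, and asking does not remove open-label bias.** Both stand. An identical question to both arms makes capture more even, but answers and judgments of relation remain unblinded, and relation to harvest can apply only to BMC. The table should therefore lead with events regardless of relation.

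**Conclusion.** The point holds in a limited form. Harms after the procedure are not systematically solicited in either arm and no summary by arm is planned, while the added harvest and heparin risks sit in the BMC arm. Following the plan as written would give harm information that depends on what patients volunteer, plus whatever the one-time questionnaire captures.

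This is a cheap improvement that should be made; it is not a flaw in the efficacy comparison. Confidence is high on what sections 5, 8 and 9 list and lower on anything that might stand in the unseen forms, consent document or appendices. The size of the loss cannot be computed, because the documents give no harm rates. A reader might also infer that adding the question would let the trial establish the safety of BMC; the zero-event limit above shows that it would not for rare harms.

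**What to change.** **Section 5.** At each of the seven existing contacts, ask both arms the same question: since the last contact (since injection, at month 1), has there been any new infection, bleeding, clot, harvest-site or knee problem, emergency or hospital visit, or further knee procedure? Log date, seriousness, relation and outcome.

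**Section 10.** Have the principal investigator or the designated team member already named there review serious events as they are reported.

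**Section 8.** Among injected patients, report by arm the number and percentage with:

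1. at least one event of any kind, regardless of relation;
2. at least one serious event;
3. as a secondary row, at least one event judged related.

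Give exact 95% intervals and, beside them, the number who answered the question, since a patient lost to follow-up is not a patient without events. Label the table descriptive, with no between-arm test. Do not count a worse WOMAC or IKDC score, or an added medication alone, as a harm.

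**Cost.** A short amendment, one extra question at contacts already scheduled, and a log kept by existing staff. No new visit, committee or change in sample size. Answers remain open-label and inherit the dropout of the email and phone contacts.

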Exclusion criteria include: Patients with major mechanical axis deviation of more than 50% into either compartment (varus or valgus) or that have had a corticosteroid injection within 3 months or a hyaluronic acid injection within 6 months will not be eligible. Patients will be excluded if they have a history of the following medical conditions - diabetes, autoimmune disorders, disorders requiring immunosuppression, rheumatoid arthritis, hemophilic arthropathy, infectious arthritis, Charcot's knee, Paget's disease of the femur or tibia, or history of cancer. In addition anyone with an ongoing infectious disease or significant cardiovascular, renal or hepatic disease will be excluded.

4 Subject Enrollment

120 patients will be recruited through physician practices and with print, flyer or web based advertisements (AREF and EmCYTE websites). Those patients who contact the clinical trials department through the physician's office or by referral from an advertisement or otherwise will be prescreened for adherence to the inclusion and exclusion criteria via phone or in person.

Once the potential participant has been prescreened for inclusion and exclusion criteria, and agreed to be screened for participation in the study they will be instructed on study enrollment protocols which will include a visit with one of the physician investigators for evaluation, x-ray's and confirmation of adherence to the inclusion criteria. Subjects will also be instructed that they must not take any prescription or over the counter non-steroidal anti-inflammatory drugs (NSAIDS) for 3 weeks prior to the evaluation appointment. Following the physician evaluation and confirmation subjects will again have all study requirements explained to them and go through the described informed consent process. The subject will then be randomly placed in one of the two study groups and be scheduled to receive either a PRP injection or BMC injection in their affected knee.

5 Study Design and Procedures

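### Sixty per group leaves 48 at the stated 20% dropout, 2 short of the 50 per group the plan requires for the IKDC; 50 are retained only up to 16.7% dropout

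*Combined protocol and SAP*

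**What the plan says.** Section 9 (Statistical Considerations) bases the sample size on earlier trials of PRP against hyaluronic acid, using averaged standard deviations "to detect average of group mean effect at 80% power". It reports two requirements: "25 patients per group would be needed to reach statistical significance with the WOMAC", and "50 patients would be needed per group for the IKDC". The next sentence gives the allowance for attrition: "Considering a potential dropout rate of 20%, 60 patients per group was chosen as the sample size".

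The enrolment figures agree with this. Section 4 (Subject Enrollment) says "120 patients will be recruited through physician practices", and section 5 (Study Design and Procedures) says "patients will be randomized into the 2 study groups of 60 each". No section provides for replacing dropouts or for any further allowance.

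The questionnaires are collected "at 1, 3, 6, 9, 12, 18, and 24 months following the injection" (section 5), and section 9 states the analysis as follows: "Data will be analyzed for differences between groups using a repeated measures ANOVA design". The plan does not say at which visit the 20% applies, or how missing visits are handled.

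**The concern.** The dropout sentence follows directly on the two requirements and gives attrition as the reason for 60. The WOMAC cannot be what drives that number: allowing for 20% dropout from 25 gives 25 / 0.80 = 31.25, so 32 per group. The allowance therefore bears on the IKDC's 50, and a reader will conclude that 50 evaluable patients per group remain after 20% dropout.

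If that is untrue, the plan overstates how much attrition its IKDC comparison can bear. This matters somewhat in a trial with 24 months of follow-up, because the allowance is the stated justification for the sample size. No primary endpoint is named and section 8 analyses both questionnaires, so the IKDC requirement cannot be set aside as secondary.

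**Working it through.** **Inputs.** All are from section 9, with the group size confirmed in sections 4 and 5: requirement 50 per group (IKDC) and 25 per group (WOMAC); dropout 20%; 60 per group, 120 in total; 80% power; significance level 0.05, sidedness not stated.

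**1. The plan's own figure.** Adding 20% to the requirement gives 50 × 1.20 = 60, which matches the plan exactly. Probably the 20% was added to the number required instead of being taken off the number enrolled. That explanation is an inference, and nothing below depends on it.

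**2. Patients remaining at 20% dropout.** 60 × (1 − 0.20) = 48 per group. Shortfall against the IKDC: 50 − 48 = 2 per group, 4 in total.

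**3. Dropout at which 50 are still retained.** 1 − 50/60 = 16.7%, that is, 10 of 60 in each group.

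**4. Size that would retain 50 at 20% dropout.** 50 / (1 − 0.20) = 62.5, rounded up to 63.
- 62 × 0.80 = 49.6, below 50.
- 63 × 0.80 = 50.4, enough.
- Total: 2 × 63 = 126, which is 6 more than the 120 planned.

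**5. WOMAC.** 48 exceeds 25, and 25 are retained up to 1 − 25/60 = 58.3% dropout.

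**6. Effect on IKDC power (context only).** The plan gives no effect size, SD or test for its power analysis, so I assume a two-sided 0.05 t test at one time point. For each possible exact requirement behind the stated 50, I solve for the standardized difference d that gives 80% power, then compute power at 48 per group from the noncentral t distribution.

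| Exact requirement per group | d | Power at 48 per group |
|---|---|---|
| 52 (rounded down to 50) | 0.5547 | 76.7% |
| 51 (rounded down to 50) | 0.5602 | 77.5% |
| 50 | 0.5659 | 78.3% |
| 49 (rounded up to 50) | 0.5717 | 79.2% |
| 48 (rounded up to 50) | 0.5778 | 80.0% |
| 47 (rounded up to 50) | 0.5840 | 80.8% |
| 46 (rounded up to 50) | 0.5905 | 81.7% |

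If 50 is exact, the loss is 80 − 78.3 = 1.7 percentage points. If 50 was rounded up from 48 or fewer, there is no loss. If it was rounded down from 51 or 52, the loss is 2.5 or 3.3 points.

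**The case against.** The arithmetic is not in dispute; the objections are about weight.

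- **Loose wording.** The plan says only that dropout was considered, and never states that 50 will remain. That is true, but attrition is the only reason it gives for choosing 60, and a reader will take the sentence as an allowance made in full.
- **Rounding.** 25 and 50 are both round numbers, so the exact IKDC requirement may have been 48 or fewer, in which case nothing is lost. This is possible, and the documents cannot settle it. It bears on the power consequence and leaves the mismatch between the stated 50, 60 and 20% as it is.
- **Partial completers.** 48 is the count once all dropout has occurred. Over seven follow-up visits, more than 48 may contribute at earlier visits, and a repeated measures analysis may use some of those data. If it is restricted to complete cases, it will not. This softens the consequence, but the plan's sizing is expressed in patients per group and takes no credit for partial data.
- **Size against other uncertainty.** A change of under 2 points of power is small beside the uncertainty in inputs borrowed from trials of a different comparison. This stands, and it is why the point is rated minor.

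**Conclusion.** The concern holds, at minor severity. On the plan's own numbers, 60 per group does not cover 20% dropout from the IKDC requirement; it covers 16.7%. This conclusion rests only on the stated 50, 60 and 20%, and confidence in it is high.

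The power consequence is much less certain. A loss of about 1.7 points applies only if 50 is exact and the assumed t test resembles the calculation actually done; the planned repeated measures ANOVA could give something different. The WOMAC comparison is unaffected. This is an incorrect statement about the sample size, with little effect on what the trial can detect.

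**What to change.** Keep 120 patients and correct the dropout sentence in section 9. It should state three things:

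- 60 per group retains the 50 per group required for the IKDC with dropout up to 16.7%;
- at 20% dropout 48 per group remain, against the stated 50;
- the WOMAC requirement of 25 per group is still met at 20% dropout.

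A back-solved power figure should not go into the plan. If the sponsor wants to state IKDC power at 48 per group, it should compute it from the effect size and SD used in its own power analysis.

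The cost is one sentence, with no extra patients and no change to design or analysis; the stated tolerance becomes slightly less favourable. If the sponsor prefers to keep the 20% allowance in full, the alternative is 63 per group, at a cost of 6 more patients. The shortfall is too small to require that.

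### Section 9 names a repeated measures ANOVA with no baseline covariate, so the pre-treatment WOMAC and IKDC scores are not used for the precision they can give

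*Combined protocol and SAP*

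**What the plan says.** Section 9 gives one between-group method: "Data will be analyzed for differences between groups using a repeated measures ANOVA design", with significance at p below 0.05. It names no covariate, visit, average over visits or covariance structure, and does not say how the pre-treatment score enters. Section 8 adds means, standard deviations and subscale scores, and says: "Additional determinations based on medication usage and failure rates will be examined as well". It names no other test.

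Under section 5 both groups complete the WOMAC and IKDC "questionnaires prior to any treatment" and again "at 1, 3, 6, 9, 12, 18, and 24 months following the injection". That is one baseline and seven follow-up scores per patient. Allocation is 60 versus 60, without blinding of patients or clinicians.

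On sample size, section 9 says: "Analysis utilized the average of standard deviation to detect average of group mean effect at 80% power". It reports 25 per group for WOMAC and "50 patients would be needed per group for the IKDC", then chooses 60 per group to allow for 20% dropout. It gives no mean difference, standard deviation or correlation.

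**The concern.** A patient's baseline questionnaire score usually predicts later scores on the same questionnaire. Taking that predictable part out of the residual narrows the confidence interval for BMC minus PRP and needs no extra data. As section 9 stands, baseline could enter in three ways:

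- not at all;
- as a change score;
- as an eighth level of the time factor, where the group main effect averages in a visit at which no treatment effect can exist.

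None of these is more precise in large samples than baseline adjustment of the same contrast. IKDC has the least slack, because 20% loss from 60 leaves 48 per arm against the 50 that the plan says it needs.

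**Working it through.** **Inputs from the documents.** 25 and 50 per group at 80% power; 60 per arm; 20% dropout; one baseline and seven follow-ups at 1, 3, 6, 9, 12, 18 and 24 months.

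**Assumptions.** Two-sided 0.05; unit variance at every visit; compound symmetry with rho 0.3, 0.5, 0.7; as an alternative, correlation decaying by a factor of 0.90, 0.95 or 0.97 per month.

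**The plan's own figures.** Without a difference and SD, 25 and 50 cannot be reproduced, only inverted. By the normal approximation d = sqrt(2/n) × (1.96 + 0.84), which gives 0.79 for n = 25 (WOMAC) and 0.56 for n = 50 (IKDC). The final size is 50 × 1.2 = 60, and 60 × 0.8 = 48 per arm remain.

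**Average of the seven follow-ups, compound symmetry.** Variance factors:
- post-only: (1 + 6rho)/7
- change from baseline: (1 + 6rho)/7 + 1 − 2rho
- baseline-adjusted: (1 + 6rho)/7 − rho²

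| rho | post-only | change | adjusted | adjusted / post-only | adjusted / change |
|---|---|---|---|---|---|
| 0.3 | 0.400 | 0.800 | 0.310 | 0.78 | 0.39 |
| 0.5 | 0.571 | 0.571 | 0.321 | 0.56 | 0.56 |
| 0.7 | 0.743 | 0.343 | 0.253 | 0.34 | 0.74 |

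**Baseline as an eighth time level.** A constant effect d becomes 7d/8 in the group main effect, with variance (1 + 7rho)/8. Dividing that variance by (7/8)² puts it on the scale of d: 0.506, 0.735, 0.963. The adjusted variance is 0.61, 0.44, 0.26 of these.

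**One visit.** Adjusted over unadjusted is 1 − rho² = 0.91, 0.75, 0.51. Adjusted over change is (1 + rho)/2 = 0.65, 0.75, 0.85. Under decay at 24 months, the correlation with baseline is 0.90, 0.95 or 0.97 to the power 24, and adjusted over unadjusted is 0.994, 0.915, 0.768.

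**Power with 48 per arm.** Noncentral F with lambda = (48/2) × d²/v, where v is the variance factor; df 1,94 unadjusted and 1,93 adjusted.
- IKDC, one visit, unadjusted: 24 × 0.56² = 7.53, power 77.5%.
- IKDC, one visit, adjusted, compound symmetry: 7.53/0.91 = 8.27, 7.53/0.75 = 10.04, 7.53/0.51 = 14.76; power 81%, 88%, 97%.
- IKDC, 24 months, adjusted, decay: 78%, 81%, 87%.
- IKDC, constant effect, seven-visit average, compound symmetry: post-only 99%, 95%, 88%; adjusted over 99% throughout. Main effect with baseline as a level: 97%, 89%, 79%.
- WOMAC at 0.8 SD, one visit, unadjusted: 24 × 0.64 = 15.36, power already about 97%.

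**Can adjustment lose precision?** In simulation with 48 per arm (20,000 runs), the adjusted-to-unadjusted variance ratio was 0.765 with slope 0.5 in both arms, 0.811 with slopes 0.2 and 0.7, 1.001 with slopes −0.3 and 0.5, and 1.013 at zero correlation. The worst case is a loss of about 1%, from estimating one extra coefficient. Bias was at most 0.002 SD.

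**The case against.** **The ANOVA may already use baseline.** If the pre-treatment score is a time level, the group-by-time test works on change. This stands against quoting only the post-only comparison: at rho 0.7 the saving against change is 26%, not 66%. It does not remove the point, because adjustment is still at least as precise for the same contrast.

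**The choice of contrast can matter more than adjustment.** This stands. Suppose the effect rises linearly to 0.56 SD at 24 months, under compound symmetry. The adjusted seven-visit average then has 56%, 55%, 65% power, a group-by-time test has 58%, 75%, 95%, and the adjusted 24-month visit has 81%, 88%, 97%. Section 1 raises concern about PRP's long-term outcomes, so a widening difference is plausible.

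**The baseline may follow disclosure of the arm.** Section 4 ends with the patient randomised and scheduled for one of the injections. Section 5 describes randomisation and then the questionnaires, without blinding. The exact order is not stated. If knowing the arm shifted baseline by an assumed 0.1 SD, a slope of 0.7 would move the adjusted contrast by 0.1 × 0.7 = 0.07 SD. A post-only contrast would not be affected. This stands as a condition on the fix.

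**Stronger readings that the documents do not support.** A reader might infer that patients with any missed visit would be dropped, that the group-by-time test would exceed 5% error, or that the ANOVA would be run in a spreadsheet. Section 8 says "All data will be entered into an excel spreadsheet for analysis", but it mentions only means and standard deviations by name. The fitting method, any sphericity correction and the software for the ANOVA are not stated, so none of these is established.

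**Conclusion.** The point holds as lost precision. For a given contrast under 1:1 allocation, baseline adjustment is at least as precise in large samples as each of the three ways in which the planned ANOVA could treat baseline. It should not be read as saying that the planned comparison is biased or invalid, or that the trial is underpowered on every reading: for a constant 0.56 SD effect the post-only average already has 88% to 99% power.

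The size rests on assumed correlations. It ranges from a large saving (variance ratio 0.34 against post-only for the seven-visit average at rho 0.7) to almost nothing (0.994 at 24 months with decay of 0.90 per month). It matters mainly for IKDC or for effects smaller than those implied. The change is worth making because the scores are already being collected, provided that baseline is recorded before the patient knows the arm.

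**What to change.** 1. In section 9, replace the repeated measures ANOVA with a mixed model for repeated measures on the seven post-injection scores. Include arm, visit, arm-by-visit, baseline score and baseline-by-visit. Analyse patients as randomised, use all available post-injection scores, and state the missing-at-random assumption.
2. In sections 4 and 5, state that the baseline WOMAC and IKDC are completed before the allocation is disclosed to the patient.
3. Name in advance one outcome (WOMAC or IKDC) and one BMC minus PRP contrast with its 95% confidence interval: the average over visits, or a single visit if a widening difference is expected.

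The cost is revised analysis wording, a rule on questionnaire timing, standard statistical software, reliance on missing at random, and about 1% loss of precision if baseline and follow-up are uncorrelated. No extra patients, visits or questionnaires are needed.
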